5.2 Inclusion criteria

Patients eligible for inclusion in this study have to meet **all** of the following criteria:

1. Patients must give written informed consent according to local guidelines prior to any screening procedures.
2. Patients must not be eligible for another ongoing INC424 clinical trial.
3. Male or female patients aged ≥ 18 years of age.
4. Patients must be diagnosed with PMF, PPV MF or PET-MF, according to the 2008 revised International Standard Criteria [Appendix I](#), [Swerdlow 2008](#), [Vardiman 2009](#), [Barosi 2008](#)), irrespective of JAK2 mutation status.
5. Patients with PMF requiring therapy must be classified as high risk (3 prognostic factors) OR intermediate risk level 2 (2 prognostic factors, no more), OR intermediate risk level 1 (1 prognostic factor, no more) with an enlarged spleen (assessment to occur at the Screening Visit).

The prognostic factors, defined by the International Working Group ([Cervantes 2009](#)) are:

- Age > 65 years;
- Presence of constitutional symptoms (weight loss, fever, night sweats);
- Marked anemia (Hgb < 10 g/dL)*;
- Leukocytosis (history of WBC $> 25 \times 10^9/L$);
- Circulating blasts $> 1\%$ (in the peripheral blood).

*A Hgb value < 10 g/dL must be demonstrated during the Screening Visit for patients who are not transfusion dependent. Patients receiving regular transfusions of packed

red blood cells will be considered to have Hgb < 10 g/dL for the purpose of evaluation of risk factors.

6. Patients with Intermediate-1 disease and splenomegaly must have a palpable spleen measuring 5 cm or greater from the costal margin to the point of greatest splenic protrusion.
7. Patients must have a peripheral blood blast count percentage of < 10%.
8. Patients with adequate liver function defined as total bilirubin or direct bilirubin $\leq 2.0 \times$ ULN and ALT $\leq 2.5 \times$ ULN.
9. Patients with adequate renal function defined as serum creatinine $\leq 2 \times$ ULN.
10. Patients with an ECOG PS of 0, 1, or 2 ([Appendix IV](#)).
11. Women of childbearing potential must have had a negative serum pregnancy test within 14 days prior to the administration of study drug.
12. Patients must have recovered or stabilized sufficiently from any adverse drug reactions associated with prior treatment before beginning treatment with INC424.

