3.4.3 Analysis of secondary endpoints

In this section the term 'percent of change from baseline' at a time T is defined as per following definition:

$$\% \text{ change at time T} = \frac{\text{Week T value} - \text{Baseline value}}{\text{Baseline value}} \times 100$$

At least 50% reduction in spleen length from baseline at any time: The proportion of patients who achieved at least 50% reduction in spleen length at any time will be displayed along with the 95% CI for proportion of reduction.

If a patient is palpable at Baseline and becomes non-palpable at post-baseline, then this post-baseline value will be imputed as 0 (zero).

The proportion of responders (achieving at least 50% reduction in spleen length at any time from baseline) will be estimated for patients whose spleen were palpable at baseline and remained palpable or became non palpable at the post-baseline visit. In addition to the FAS, this analysis will also be done by the PPS.

Time to response is defined as the time between date of start of treatment to the date of first response. Response is defined by the 50% reduction in spleen length from baseline. Summary statistics for those responders will be provided.

Duration of response is defined as the time between date of first response ($\geq 50\%$ reduction in spleen length from baseline) to date of loss of response or death due to MF. Loss of response is defined as going back to baseline level after first time $\geq 50\%$ reduction in spleen length from baseline. In case a patient does not have loss of response or death due to myelofibrosis by the data cutoff date, DOR will be censored at the date of the last adequate assessment of spleen length OR cut-off date whichever occurs first.

Best overall response to treatment as assessed by spleen palpation is defined by the investigator.

Best overall response is defined as the best response observed during the study follow-up period. The proportion of patients in the best overall response category will be summarized.

In addition, best overall response will be evaluated and summarized by the IWG MRT criteria given in Section 3.11.2.

Change of spleen length from Baseline to end of each visit/month of therapy and at end of treatment. The change in spleen length from Baseline to end of each visit/month of therapy and at end of treatment will be described using descriptive statistics and by relevant change categories:

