3.11 Other topics

3.11.1 Handling of missing data

Patients with missing baseline values where a change from baseline is calculated or when the baseline is used as a covariate will be excluded from the analysis of that variable. Missing values in the QoL will be handled following the instruction of the instruments.

[figure not shown]
3.11.2 Table of Spleen Response and Loss of Response Criteria by IWG MRT criteria

Patients with spleen length at baseline	Response criteria	Loss of response criteria 1
Less than 5 cm	Non evaluable for response	Non evaluable for loss of response
Between 5 and 10 cm	Responder: achieve non palpable spleen	Splenomegaly 5 cm or more
	Stable disease: does not meet criteria for response NOR for disease progression	Meet criteria of progressive disease
	Progressive disease: increase of 100% from baseline	-
More than 10 cm	Responder: reduction of 50%	Loss of the 50% reduction
	Stable disease: does not meet criteria for response NOR for	Meet criteria of progressive disease

[figure not shown]
	disease progression	
	Progressive disease: increase of 50% from baseline	-

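### The any-time ≥50% spleen responder analyses set no minimum baseline length, so they include 1–4 cm spleens in which a 1–2 cm lower reading already counts as a response

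*SAP*

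**What the plan says.** SAP 3.4.3 plans a responder proportion with a 95% CI. A responder is a patient "achieving at least 50% reduction in spleen length at any time from baseline", and the proportion "will be estimated for patients whose spleen were palpable at baseline and remained palpable or became non palpable at the post-baseline visit". A spleen that becomes non-palpable is set to 0 cm. No minimum baseline length is set and no second reading is required. SAP 3.4.4.2 adds that scheduled and unscheduled assessments are all used unless stated otherwise. Time to response and duration of response in SAP 3.4.3 both start from the first such reading, and response is lost on return to the baseline length.

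SAP 3.4.3 also says: "In addition, best overall response will be evaluated and summarized by the IWG MRT criteria given in Section 3.11.2". In that table a baseline below 5 cm is "Non evaluable for response", 5–10 cm requires a non-palpable spleen, and more than 10 cm requires a 50% reduction.

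At entry (Protocol 5.2), "Patients with Intermediate-1 disease and splenomegaly must have a palpable spleen measuring 5 cm or greater from the costal margin". No spleen minimum is stated for intermediate-2 or high-risk patients. SAP 2.2 plans no subgroup analyses.

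**The concern.** A 50% relative cut-off means something different at each baseline length. In whole centimetres the readings that qualify are 1→0, 2→1, 3→1 and 4→2, so a fall of 1 or 2 cm is enough. A 5 cm spleen must fall by 3 cm and a 12 cm spleen by 6 cm. The measurement is manual palpation with a soft ruler (Protocol 8.3.1.1), and one low reading is never revisited. Because the rule takes the lowest reading over all visits, the chance of a false response grows with the number of readings, and patients followed longer have more of them.

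At stake is how the responder proportion and its CI can be interpreted, together with the two time-based summaries. In a 1 cm spleen, readings of 1, 0, 1 give a response followed by a loss of response with no change in the patient. Nothing planned would show this. There is no breakdown by baseline length, and the per-protocol repeat excludes only on age, diagnosis and fibrosis grade (SAP 2.1).

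**Working it through.** The plan states no palpation error, expected response rate or sample size calculation, so there is no figure of its own to reproduce.

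**From the documents.** Visits at Weeks 4, 8, 12 and then every 12 weeks (SAP 2.3) give 3 readings by Week 12, 6 by Week 48 and 10 by Week 96. Response is any reading ≤ 0.5 × baseline. The length bands <5, 5–10 and >10 cm are those of SAP 3.11.2.

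**Assumed, not in the documents.** Palpation SD s = 0.5, 1.0 or 1.5 cm; normal errors, independent between visits; no true change.

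**Closed form.** Take the recorded baseline b as true, with error at the k follow-up readings only:

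P(false response) = 1 − [1 − Φ(−(b/2)/s)]^k

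- b = 2, s = 1, k = 10: Φ(−1) = 0.159; 1 − 0.841^10 = 82%
- b = 4, s = 1, k = 10: Φ(−2) = 0.023; 1 − 0.977^10 = 21%
- b = 5, s = 1, k = 10: Φ(−2.5) = 0.0062; 1 − 0.9938^10 = 6%
- b = 5, s = 1.5, k = 10: Φ(−1.667) = 0.048; 1 − 0.952^10 = 39%

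Averaged equally over 1, 2, 3 and 4 cm, this runs from 12% (s = 0.5, k = 3) to 84% (s = 1.5, k = 10).

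**Simulation.** This adds error in the baseline reading and whole-cm recording floored at 0. True length is uniform on 0–25 cm and unchanged; 2,000,000 patients. Chance of at least one response at 3 / 6 / 10 visits:

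| Baseline reading | SD 0.5 cm | SD 1.0 cm | SD 1.5 cm |
|---|---|---|---|
| 1–4 cm | 25 / 33 / 39% | 43 / 56 / 64% | 51 / 65 / 74% |
| 5–10 cm | <1% throughout | 4 / 7 / 9% | 14 / 21 / 27% |
| >10 cm | 0% | ≤0.01% | 0.2 / 0.5 / 0.7% |

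At one fixed visit the 1–4 cm figures fall to 13%, 23% and 27% for the three SDs.

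**Correlated errors.** If half the error variance is shared across a patient's readings (assumption), the 1–4 cm figures at 10 visits fall from 39 / 64 / 74% to 27 / 51 / 65%.

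**Effect on the overall rate.** If a share f of palpable patients have 1–4 cm spleens, a proportion r of those truly respond, and q is the false-response chance in the rest, error adds f(1 − r)q. The documents give neither f nor r. With q = 64% and f assumed at 10% to 30%, the result is 6 to 19 points if r = 0. If r is assumed at 50% to 70%, it is 1.9 to 3.2 points at f = 10% and 5.8 to 9.6 points at f = 30%. The answer is set by the assumptions.

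**The case against.** The strongest reply is that this is a descriptive, exploratory analysis with no decision attached. The primary endpoint is AE incidence (SAP 3.4.1), the efficacy objective is investigator-assessed best overall response (SAP 1.2.2), and no hypotheses are tested (Protocol 11). The SAP also already plans the IWG-MRT summary, in which these spleens are not evaluable, and by-visit change categories that include ≤ −50%. All of this stands, and it limits the importance of the point.

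Four stronger readings might be inferred and are not supported:

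- *Palpation error alone produces a response in most 1–4 cm patients.* That depends on an SD the documents do not give. In the simulation it fails at SD 0.5 cm for every visit count tested (39% at 10 visits), and at SD 1.0 cm with 3 visits (43%).
- *The two spleen definitions contradict each other.* The SAP introduces the IWG-MRT criteria as an additional summary of best overall response. It is a second, stricter definition, and it also differs at 5–10 cm.
- *This is the headline efficacy result.* The documents do not give it that status.
- *Error adds a known number of points to the overall rate.* Multiplying the false-response chance by an assumed share treats every 1–4 cm patient as a true non-responder. Protocol 1.3.5 reports a 56% mean fall in palpable length at 48 weeks in one phase III trial, so true responses are probably common.

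What remains is that the any-time analyses mix lengths at which the criterion is reasonably robust to reading error with lengths at which it may not be, and no planned table separates them.

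**Conclusion.** The point holds as a limited one. The any-time ≥50% proportion, time to response and duration of response include baseline spleens of 1–4 cm on the strength of one unconfirmed reading 1–2 cm lower. With no true change, error alone could give a response in about 25% to 74% of such patients, against 0% to 27% at 5–10 cm and below 1% above 10 cm. These figures rest on an assumed SD of 0.5–1.5 cm, independent whole-cm readings and 3–10 visits; correlated errors lower them. The contrast between length bands is firmer than any single percentage. The effect on the overall rate cannot be sized, because neither the share of 1–4 cm spleens nor their true response rate is documented. The change is worth making because it is cheap; the primary analysis is not affected.

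**What to change.** In SAP 3.4.3:

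- Base the any-time responder proportion, time to response and duration of response on patients with baseline spleen ≥5 cm, the evaluability limit already in SAP 3.11.2.
- Show baseline <5 cm as a separate descriptive row, and present 5–10 cm and >10 cm separately.
- Report the Week 24 proportion with ≤ −50% change, available from the planned by-visit categories, beside the any-time proportion and in the same length bands.

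The cost is SAP wording and one table shell, with no new data. The denominator shrinks and the rate will probably be lower. The 5 cm limit does not remove the artefact entirely: at exactly 5 cm with SD 1.5 cm and 10 visits, the false-response chance is still 39% by the closed form and 45% in the simulation. That is the reason for the 5–10 cm row and the fixed-visit rate. A supplementary count requiring the next reading to confirm the response would reduce it further, if wanted.

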11.6.1.1 Full analysis set will be used for all efficacy analyses

The following endpoints are considered in assessing efficacy of INC424 in the study population.

Best overall response to treatment as assessed by spleen palpation, is defined by the investigator.

Change of spleen length from Baseline to end of each visit and at end of treatment. This parameter is computed by dividing the difference of spleen length at assessment time and at baseline by the length at baseline multiplied by one hundred.

WBC and platelet count changes from Baseline at end of each visit and at end of treatment. For each parameter, the percent of change will be computed by dividing the difference of value at assessment time and at baseline by the value at baseline, and multiplying by one hundred.

Shift in fibrosis in the bone marrow from Baseline, is defined as the status change of fibrosis at time of worst/best response (whenever it occur) compared to fibrosis status at baseline. Assessment of fibrosis in the bone marrow after enrollment is not mandatory.

Progression free survival (PFS) is the time from first study drug administration to date of documented progression (based on International Working Group for Myelofibrosis Research and Treatment Response Criteria, IWG-MRT) ([Tefferi A, Barosi G, Mesa RA, et al \(2006\)](#)) or deaths. Time will be censored at the last date the patient is known to be free of disease progression for patients without event.

Leukemia free survival (LFS) is the time from the first study drug administration date to: the date of the bone marrow blast count $\geq 20\%$ OR the date of the first peripheral blood blast count $\geq 20\%$ that is subsequently confirmed to have been sustained for at least 8 weeks or the date of death, whichever occurs first. LFS will be computed whenever data of bone marrow blast and/or peripheral blood blast counts is/are available. Time will be censored at the last date the patient is known to be free of leukemia for patients without event.

Overall survival (OS) is the time from first study drug administration to date of deaths (whatever the cause). Time will be censored at the last date the patient is known to be alive for patients without event.

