2.1 Analysis sets

Full Analysis Set (FAS) consists of all patients who received at least one administration of study drug.

Safety Set (SS) consists of all patients who received at least one dose of study drug and had at least one post-baseline safety assessment.

Please note: the statement that a patient had no adverse events (on the Adverse Event CRF) constitutes a safety assessment. Patients who have received at least one dose of study drug but who have no post-treatment safety data of any kind would be excluded from the safety population.

Per protocol set (PPS) consists of all FAS patients without any major protocol deviation.

The following major protocol deviations will lead to exclusion from the PPS:

- Male or female patients aged < 18 years of age at screening (Deviation code: I03)
- Unconfirmed diagnosis of PMF, PPV-MF or PETMF at screening (Deviation code: I04).
- Secondary MF (PPV-MF or PETMF) grade 0 and 1 for Fibrosis on scale 0-3. or grade 0, 1 and 2 on scale 0-4 at screening (Deviation code: I13).

The Full analysis set will be used for all population and efficacy analyses, while Safety set will be used for treatment administration description and safety analyses.

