3.4.4.1 Handling of missing values/discontinuations in efficacy analyses

No imputation for missing data will be performed.

Patients with missing baseline assessments will be excluded from analysis where baseline value is required to compute the corresponding endpoint.

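### The ≥50% spleen-length response rate carries the full-analysis-set label, but its denominator appears to omit treated patients never palpated after baseline, which can only raise the rate

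*SAP*

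**What the plan says.** SAP 2.1 defines the analysis set by dosing alone: "Full Analysis Set (FAS) consists of all patients who received at least one administration of study drug". No post-baseline assessment is needed to enter it. The same section assigns it to efficacy: "The Full analysis set will be used for all population and efficacy analyses". Protocol 11.6.1.1 agrees: "Full analysis set will be used for all efficacy analyses".

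SAP 3.4.3 then describes the ≥50% spleen-length analysis. Its opening sentence gives the proportion of patients reaching that reduction at any time, with a 95% confidence interval and no restriction. Two paragraphs later the responder proportion is estimated "for patients whose spleen were palpable at baseline and remained palpable or became non palpable at the post-baseline visit". The sentence after that attaches the set labels: "In addition to the FAS, this analysis will also be done by the PPS".

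On missing data, SAP 3.4.4.1 states: "No imputation for missing data will be performed". The exclusion it writes down concerns baseline only: "Patients with missing baseline assessments will be excluded from analysis where baseline value is required to compute the corresponding endpoint". SAP 3.11.1 likewise covers a missing baseline. The one imputation in the spleen analysis sets a spleen found to be non-palpable after baseline to zero; it does not deal with a spleen that was never examined again. SAP section 4, on changes from the protocol, lists the transfusion definitions and nothing about this denominator.

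**The concern.** A patient never palpated after baseline has neither remained palpable nor become non-palpable, so the restricting sentence leaves that patient out. Nothing elsewhere in the SAP brings the patient back as a non-responder. The result would be reported under an FAS label while resting on an assessed-patients subset.

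Such patients are foreseen. Protocol 7.2.1 puts the first on-treatment palpation at Week 4. SAP 2.1 allows for treated patients with no safety data after treatment starts, Protocol 7.6 for patients who decline a final visit, and Protocol 6.2.6 asks only for reasonable efforts to bring back those who stop. A patient who dies before Week 4 is an event for PFS and OS under SAP 3.4.3 but would be absent from the response rate.

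At stake is a one-directional error in a headline efficacy figure of a single-arm study. The planned confidence interval would not reflect it. The per-protocol repeat is no check, because it uses the same restriction and its listed exclusions concern age, diagnosis and fibrosis grade.

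**Working it through.** The documents state no response rate, no share of unassessed patients and no sample-size calculation, so there is no planned figure to reproduce. The check is how far the denominator rule can move the rate.

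**Notation.** N_b = treated patients with a palpable spleen at baseline; d = share of them with no later palpation; r = responders.

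- Rate under the SAP rule: p_SAP = r / [N_b(1 − d)]
- Rate among all treated, baseline-palpable patients: p_all = r / N_b
- Hence p_all = p_SAP(1 − d). The overstatement is p_SAP × d, and the ratio p_SAP / p_all is 1/(1 − d).

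An unassessed patient can never be in r, so the overstatement cannot be negative. It is zero only if d = 0.

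**Inputs.** Protocol 4.1 gives 2238 enrolled. This is an upper limit for N_b: the 5 cm palpable-spleen requirement in Protocol 5.2 applies to intermediate-1 patients, so others may enter without a palpable spleen. I also use 90% of it, 0.9 × 2238 = 2014. Assumptions, not in the documents: p_SAP of 55% (range 40% to 70%) and d from 1% to 10%.

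**Results for N_b = 2238, p_SAP = 55%**, in whole patients. The half-width is 1.96 × √[p(1 − p)/n], with n the number assessed.

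| d | Assessed | Responders | SAP rule | All treated, palpable | Overstatement (points) | 95% half-width (points) | Ratio |
|---|---|---|---|---|---|---|---|
| 1% | 2216 | 1219 | 55.0% | 54.5% | 0.5 | 2.1 | 1.010 |
| 3% | 2171 | 1194 | 55.0% | 53.4% | 1.7 | 2.1 | 1.031 |
| 5% | 2126 | 1169 | 55.0% | 52.2% | 2.8 | 2.1 | 1.053 |
| 10% | 2014 | 1108 | 55.0% | 49.5% | 5.5 | 2.2 | 1.111 |

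At a 55% rate the overstatement matches the half-width near d = 2.1/55 = 3.8%.

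**Range over assumed rates of 40% to 70%** (p_SAP × d): 0.4 to 0.7 points at d = 1%, 1.2 to 2.1 at 3%, 2.0 to 3.5 at 5%, and 4.0 to 7.0 at 10%.

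**Smaller N_b.** Apart from rounding to whole patients, the overstatement does not depend on N_b. With N_b = 2014 and a 55% rate, the half-width for d of 1% to 10% is 2.2 to 2.3 points.

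**Wording check.** SAP 3.4.3 uses almost the same phrase for the by-visit change in spleen length, where it refers to the visit under consideration. A value at that visit is needed there, so the condition makes sense. A response at any time has no single post-baseline visit, so the condition does not fit this endpoint.

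**The case against.** The strongest reply is that few patients will be lost. Protocol 7.6.2.1 requires palpation at the early-termination visit, Protocol 7.6.3.1 requires it again at the 28-to-37-day follow-up, and SAP 3.4.4.2 uses unscheduled as well as scheduled assessments. This stands. A reader might infer that everyone stopping early for toxicity or progression disappears from the denominator. The documents do not support that: most of these patients should have a palpation when they stop. The group at risk is mainly early deaths, losses to follow-up and refusals to return.

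Second, the text is not unambiguous. The opening sentence of the analysis has no restriction, and the later phrase could be read as merely separating spleens palpable at baseline from those that were not. This stands in part. Exclusion is the more natural reading, and under either reading no rule counts the unassessed patient as a non-responder.

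Third, a reader might infer that the named secondary objective is affected. It is not shown to be. SAP 1.2.2 names best overall response as judged by the investigator, and SAP 3.4.3 treats that as a separate item without this restriction. Protocol 3.3.2 does describe best overall response through percentage change in spleen length, so the two are related, but the SAP does not equate them.

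Fourth, a reader might compare the rate with other trials that count unassessed patients as failures. The documents do not say how other trials handled them, and the point does not need that comparison.

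Leaving out patients with no palpable spleen at baseline is sound, since a percentage change from zero is undefined.

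**Conclusion.** The point holds for the ≥50% spleen-length reduction rate. On its natural reading, SAP 3.4.3 applies a narrower denominator than its FAS label, without declaring the narrowing. The direction is certain whenever any baseline-palpable treated patient has no later palpation; if there are none, there is no effect.

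The size cannot be fixed from the documents. It rests on the assumed d and on the assumed rate under the SAP rule. With d of 1% to 3%, which the required termination and follow-up palpations make plausible, the shift at a 55% rate stays inside the confidence half-width. At 5% or more it exceeds it. A claim of large inflation would therefore go beyond the text. The analysis is descriptive, so no test result is at risk; what is affected is the accuracy of a reported rate and its interval.

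**What to change.** Rewrite the denominator sentence in SAP 3.4.3:

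- For the main analysis, use all FAS patients with a palpable spleen at baseline; for the repeat, all per-protocol patients with a palpable spleen at baseline.
- Count patients with no post-baseline palpation as non-responders.
- Report their number.
- Keep the assessed-only proportion as a supportive analysis, labelled as such.

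This changes one sentence and adds one count to the table. It needs no new data. The cost is a slightly less favourable rate.

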$\leq -50\%$, (-50%, -25%], (-25%, -5%], (-5%, 5%], (5%, 25%], (25%, 50%] and $\geq 50\%$

The descriptive summary will include the mean, standard deviation, median, minimum, maximum and 95% CI of the mean over time and at EOT visit for patients who were palpable at baseline and remained palpable or non-palpable at the post-baseline visit considered. In addition, number (n) of patients who remain non palpable, or became palpable from non-palpable at baseline will also be displayed.

WBC and platelet count changes from Baseline at end of each visit/month of therapy and at end of treatment. For each parameter, the percent of change will be computed by dividing the difference of value at assessment time and at baseline by the value at baseline, and multiplying by one hundred. WBC and platelet count changes from baseline will be summarized at end of each visit of therapy and at end of treatment.

Shift in fibrosis in the bone marrow from Baseline, is defined as the status change of fibrosis at time of worst/best response (whenever it occur) compared to fibrosis status at baseline.

Assessment of fibrosis in the bone marrow after enrollment is not mandatory and a listing will be provided with the results of the bone marrow biopsy (if performed).

Progression free survival (PFS) is the time from first study drug administration to date of documented progression (based on International Working Group for Myelofibrosis Research and Treatment Response Criteria) or deaths. Time will be censored at the last date the patient is known to be free of disease progression for patients without event. Deaths on or before the follow up/study completion evaluation visit (on-treatment and post-treatment deaths – Section 3.4.1.2) will be considered in the analyses.

Leukemia free survival (LFS) is the duration from first study drug administration to date of documented leukemia. Observation will be censored, if leukemia is not observed before the

end-of-study, death or lost to follow-up, at last date the patient is known to be free of leukemia. Deaths on or before the follow up/study completion evaluation visit (on-treatment and post-treatment deaths – Section 3.4.1.2) will be considered in the analyses.

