Overall survival (OS) is the duration from first dose of study drug administration to the date of death due to any cause. If a patient is alive at the time of data cutoff, OS time will be censored at the time of last contact that is no later than the follow up/study completion evaluation visit. In case of early termination due to any reason, OS observation will be censored at the last contact date. Deaths on or before the follow up/study completion evaluation visit (on-treatment and post-treatment deaths – Section 3.4.1.2) will be considered in the analyses.

Method of analysis of secondary endpoints

The proportion of patients by best overall response category will be summarized. Proportion of responders will be estimated and its 95% confidence intervals provided.

Change in spleen length from Baseline to end of each visit/month of therapy and at end of treatment will be described using descriptive statistics and by relevant change categories (e.g. ($\leq 50\%$), ($-50\%, -25\%$], ($-25\%, -5\%$], ($-5\%, 5\%$], ($5\%, 25\%$], ($25\%, 50\%$] and $>50\%$).

WBC and platelet count changes from baseline will be summarized using descriptive statistics at the end of each visit and at the end of treatment.

Listing of patients with bone marrow biopsy will be provided with fibrosis status.

PFS, LFS, and OS will be estimated with the Kaplan Meier method and 95% confidence intervals will be provided for the estimated median.

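### Duration of spleen response ends only at loss of response or death due to MF; responders who die of another cause are censored, so the estimate is not the probability of being alive and still in response

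*SAP*

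**What the plan says.** SAP section 3.4.3 starts duration of response (DOR) at the first palpable spleen length reduction of at least 50% and ends it "to date of loss of response or death due to MF". On the first of these: "Loss of response is defined as going back to baseline level after first time" reaching that reduction.

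The censoring rule is triggered as follows: "In case a patient does not have loss of response or death due to myelofibrosis by the data cutoff date". Then: "DOR will be censored at the date of the last adequate assessment of spleen length OR cut-off date whichever occurs first". A responder who dies of a cause other than MF meets the trigger and is censored. No other part of the protocol or SAP adds such deaths back.

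Two neighbouring endpoints in section 3.4.3 treat death differently. The PFS entry reads "Treatment Response Criteria) or deaths. Time will be censored at the last date the patient is known to be free of disease progression", with no restriction on cause. OS runs "to the date of death due to any cause". Both also state which deaths qualify: those up to the follow-up/study completion visit. DOR has no such window.

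The methods paragraph that closes section 3.4.3 names Kaplan-Meier for PFS, LFS and OS. It names no estimator for DOR. DOR is not among the efficacy endpoints in protocol sections 3.3.2 and 11.6.1.1, and SAP section 4 does not list it as a change.

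**The concern.** A patient who has died cannot later lose response, so a death from infection, bleeding or a cardiac event is a competing event. The rule instead treats it as ordinary censoring, as if the patient could still be followed for loss of response. A reader of a durability figure will usually take it as the chance that a responder is alive and still responding. The rule does not estimate that chance.

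The result also depends on who decides that a death was due to MF. The SAP does not define the term and describes no adjudication. Protocol section 9.1.1 collects deaths on a Death form. The same section asks for septic shock occurring when AML is found to be reported separately from progression. Whether such a death ends the response or is censored is left open.

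Nothing confirmatory is at stake. In a descriptive study, though, the reported estimate is the result.

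**Working it through.** The plan states no expected DOR, so there is no figure to reproduce. The check asks what the rule estimates and how far that could lie from the two natural alternatives.

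**Inputs (all illustrative)**
- Loss of response: protocol section 1.3.5 reports 80% of COMFORT-II responders still in response at a median follow-up of 12 months. Read as a one-year proportion, h_loss = −ln(0.80) = 0.223 per year.
- Death from any cause: protocol section 1.3.5 reports 13 deaths (8.4%) on INC424 in COMFORT-I at a median of 51 weeks. h_death = −ln(1 − 0.084) / (51/52) = 0.089 per year, varied from half to one and a half times.
- Share of deaths not due to MF: not in the documents; assumed 25%, 50% and 75%.

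**Formulas (constant hazards, h_death = h_MF + h_nonMF)**
- SAP rule with Kaplan-Meier: S_SAP(t) = exp(−(h_loss + h_MF)t)
- Alive and in response: S_all(t) = exp(−(h_loss + h_death)t)
- Ratio: S_SAP / S_all = exp(h_nonMF × t), never below 1
- Free of loss or MF death, with non-MF death as a competing event: 1 − [(h_loss + h_MF)/(h_loss + h_death)] × [1 − S_all(t)]

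**Base case at 24 months, half of deaths non-MF (h_MF = h_nonMF = 0.0447)**
- S_SAP = exp(−2 × 0.2679) = 58.5%
- S_all = exp(−2 × 0.3126) = 53.5%
- Competing-risk version: 1 − (0.2679/0.3126) × (1 − 0.535) = 60.2%

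**Range at 24 months (%)**

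| h_death per year | Non-MF share | SAP rule | Alive and in response | Excess (points) | Competing-risk version |
|---|---|---|---|---|---|
| 0.045 | 25% | 59.8 | 58.5 | 1.3 | 60.3 |
| 0.045 | 50% | 61.2 | 58.5 | 2.7 | 62.0 |
| 0.045 | 75% | 62.6 | 58.5 | 4.1 | 63.7 |
| 0.089 | 25% | 56.0 | 53.5 | 2.4 | 56.8 |
| 0.089 | 50% | 58.5 | 53.5 | 5.0 | 60.2 |
| 0.089 | 75% | 61.2 | 53.5 | 7.7 | 63.5 |
| 0.134 | 25% | 52.3 | 48.9 | 3.4 | 53.7 |
| 0.134 | 50% | 56.0 | 48.9 | 7.0 | 58.5 |
| 0.134 | 75% | 59.8 | 48.9 | 10.9 | 63.3 |

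The excess is taken from unrounded values. At 12 months the base case gives 76.5% against 73.2%.

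**Visit schedule.** A simulation of the base case with 12-weekly visits, censoring at the last visit before a non-MF death, gives 77.8% against 74.3% at 12 months and 60.5% against 55.3% at 24 months. The gap is about the same.

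**Attribution alone.** Keep the deaths fixed at 0.089 per year and change only their label. If all are called MF deaths, the SAP-rule estimate at 24 months is 53.5% and the median is ln 2 / 0.3126 = 2.22 years. If none are, the figures are 64.0% and ln 2 / 0.2231 = 3.11 years.

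**The case against.** The strongest reply is that a cause-specific DOR is a legitimate target, not an arithmetic error. That stands. A reader might infer that the estimate is simply too high, but this holds only against being alive and in response. Against the competing-risk version it is low in every row of the table, by about 0.5 to 3.5 points.

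A reader might also take a Kaplan-Meier curve as planned. It is a fair inference from the censoring rule, but the SAP does not say so.

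Nor is DOR the only endpoint with unusual death handling. The LFS entry lists death among the reasons for censoring and then says deaths within the follow-up window will be considered. The contrast is therefore with PFS and OS, not with the whole section.

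The size is assumed. COMFORT-II response was a spleen volume reduction of at least 35%. Here it is a palpable length reduction of at least 50%, lost only on return to baseline, so the rate may not transfer. Responders may also not die at the rate of all treated COMFORT-I patients. The documents do not give the number of responders, so the gap cannot be set against a standard error.

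It is tempting to say that drug-related deaths lengthen the apparent effect. A censored patient adds no response time after the last spleen assessment, and these deaths still appear in the death summaries, PFS and OS. The open-label design adds little, since with one arm there is no between-arm attribution bias. What remains is the undefined term and the absence of adjudication.

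**Conclusion.** The point holds in a limited form. As written, a non-MF death in response is censored. With Kaplan-Meier, the result is neither the probability of being alive and in response nor the competing-risk probability of avoiding loss or MF death. Relative to the first, the direction is certain. The 24-month excess of about 1 to 11 points is illustrative and rests on constant hazards borrowed from COMFORT and an assumed 25% to 75% non-MF share. The dependence on an undefined attribution follows from the text alone.

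DOR is descriptive, appears only in the SAP and carries no hypothesis test. The primary analysis of treatment-emergent adverse events is unaffected. This is a cheap improvement, not a defect that threatens the study's main results.

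**What to change.** In SAP section 3.4.3:
- Define the DOR event as the first of loss of response or death from any cause.
- Apply the same death window as for PFS.
- Censor only patients who are alive and in response.
- Name Kaplan-Meier as the estimator.

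If the MF-death version is kept, report it as secondary, define death due to MF, and give cumulative incidences of loss of response and of death as competing events. The two remedies move the figure in opposite directions, so the SAP should say which quantity each one estimates.

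The cost is SAP wording. Death dates are already needed for OS and the death summaries. The downside is a slightly shorter reported duration of response.
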